Chronic kidney disease has been reported in 17% of HIV positive patients, and increasing age is an independent risk factor¹⁶. Glomerular filtration rate declines with age, and people over 60 years have 20–30% lower GFR than those under 50 years¹⁷. Age-related decline in renal function is associated with co-morbidities including hypertension, diabetes mellitus, and atherosclerotic, cardiovascular and urological disease¹⁸. Serum phosphate levels decline with age as a result of impaired tubular phosphate reabsorption¹⁹ and declining muscle mass results in lower serum creatinine concentrations. Elderly patients often use multiple medications, many of which are excreted via the kidney. Altered body composition and impaired renal function contribute to altered pharmacokinetics and pharmacodynamics in older patients, and may lead to an increased incidence of nephrotoxicity and systemic side effects. In addition, renal failure and altered renal tubular function may affect bone mineralisation.

Musculoskeletal

Research into musculoskeletal manifestations and pain has been neglected in HIV-positive adults. A recent survey in Brighton of >850 respondents found a prevalence of current pain of 63%, with 80% of those with pain having had symptoms for >3 months and one in 4 of these patients meeting the criteria for chronic widespread pain²⁰. In HIV-negative adults, chronic widespread pain is associated with an excess risk of mortality from cancers and cardiovascular disease²¹. Worldwide, osteoarthritis affects 60% of adults aged >65 years and is a major cause of disability; neither the prevalence nor impact of osteoarthritis have been assessed in HIV-positive adults.

Menopause

Around a third of those living with HIV in the UK are female. Whilst HIV appears to be associated with an earlier onset of the menopause²², the clinical implications of this for cognitive function, BMD and fracture risk, cardiovascular disease and lipid/glucose metabolism²² are unclear.

Antiretroviral drug use

Older individuals starting cART generally experience better virological responses but poorer immunological and clinical outcomes than their younger counterparts²³. Laboratory abnormalities and temporary discontinuations of cART due to toxicities are common^{23,24}. Detailed prospective studies on the pharmacokinetic characteristics of antiretroviral drugs are required to determine the optimal drug concentration and toxicity threshold in this population.

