Older individuals experience changes in several elements of drug pharmacokinetics, including absorption, distribution, metabolism, and elimination. Furthermore, older HIV-positive people may be treated with several therapeutic agents that may interact with antiretroviral drugs²⁵. Data from other drugs suggest that elderly patients require lower doses to achieve therapeutic efficacy but may experience adverse events at lower concentrations. Plasma concentrations of some HIV protease inhibitors are higher in those aged >40 years²⁵.

Transmembrane drug transporter (i.e. p-glycoprotein) expression and function increases with older age, which may contribute to altered drug effects, drug toxicity and drug-drug interactions. Finally, reduced glomerular filtration rate that may occur in older people may lead to impaired elimination of drugs undergoing renal excretion, resulting in increased potential for toxicity.

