3.3 Justification for the study

Currently, there is no large study on HIV and the effects of ageing in the UK and Ireland. Internationally, several research groups have developed initiatives in this area, but most of these studies are either limited by size, or are still at the recruitment stage. For example, the Hawaii Aging with HIV (HAWH) cohort has been running for several years but includes only around 60 HIV-positive individuals. Furthermore, studies are often hampered by the lack of appropriately selected and matched control groups, which limits the conclusions that can be reached regarding any associations with age and/or HIV status.

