4.0 Study Plan

Aim:

1. To analyse the incidence and outcomes of co-morbidities in older-HIV-positive people and their relationship with demographic/clinical factors.
2. To evaluate associations between antiretroviral drug concentrations and age, and to assess the potential impact of age on drug efficacy, drug-drug interactions and co-morbidities.
3. To contribute to the development and implementation of evidence-based recommendations for the clinical monitoring of older HIV-positive patients.

Design:

Multicentre, prospective, observational study over 3 years

Our study will describe the impact of advancing age on the experience of living with HIV in England and Ireland. To address this we will establish cohorts of HIV-positive people aged >50 and <50 years as well as demographically matched HIV-negative people aged >50 years.

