4.2.1 Recruitment of HIV-positive cohorts

A list of individuals eligible for the older HIV-positive cohort will be generated at each clinic by study co-ordinators in collaboration with the lead consultant at the clinic, thus ensuring no unnecessary transfer of patient identifiable data out of the clinic. Patients will be randomly sampled from the list, with black African heterosexual men and women, and white heterosexuals (men or women) being over-sampled so that the final cohort includes 100 participants in each of these three groups. Clinic lists of younger patients attending each clinic will be stratified by age, gender, ethnicity and sexual orientation; eligible patients will then be sampled from these lists at a rate determined by the demographic profile of the older patients at the clinic.

Recruitment targets at each clinic are shown below in table 2:

Table 2: Recruitment targets at each site

Centre	Patients seen in 2008/09		Recruitment targets			Total
	<50 years	>50 years	HIV positive years	HIV negative years	>50 years	
St. Mary's Hospital	1406	317	60	120	60	240
King's College Hospital	1264	207	40	80	40	160
Chelsea & Westminster Hospital	3146	902	190	380	190	760
Homerton Hospital	445	73	15	30	15	60
Mortimer Market Centre	2246	468	90	180	90	360
Brighton and Sussex Hospital	1159	386	80	160	80	320
Mater Misericordiae University Hospital Dublin	536	65	25	50*	25	100
Total	10202	2418	500	1000	500	2000

*these subjects are already recruited into the Dublin HIV cohort study, therefore high rates of recruitment are considered feasible.

The recruitment target for Royal Free Hospital, open for recruitment as of November 2015, is as follows: 25 patients > 50 years HIV-positive; 13 patients < 50 years HIV-positive; and 13 HIV-negative controls (total of 51).

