4.3 Study Objectives

Clinical manifestations

- To describe the incidence and presenting features of serious medical conditions (such as cardiovascular, liver, renal disease, cancer and fragility fractures) in the three cohorts.
- To describe the outcomes of serious medical conditions (including time to recovery/resolution, where applicable, the incidence of complications and use of health-care).
- To compare NC function in the three cohorts, and to identify predictors of NC function.
- To compare the levels of musculoskeletal pain in the three cohorts, to identify predictors of this and to describe the health-care needs of those affected.
- Among women, to assess the effects of menopausal status on cardiovascular disease, BMD and lipid/glucose metabolism.

Antiretroviral pharmacokinetics and drug interactions

- To describe plasma (or, where appropriate, intracellular) concentrations of antiretroviral agents (tenofovir, non-nucleoside reverse transcriptase, protease, integrase and entry inhibitors) at baseline in the older HIV-positive cohort, and to compare these to those seen in younger HIV-positive patients.
- To describe the incidence of toxicities/drug discontinuations and immunological/virological responses to cART in the HIV-positive cohorts and to assess correlations between these events and plasma drug concentrations.
- To describe the level of poly-pharmacy in the older HIV-positive cohort and thus the potential for/prevalence of unwanted drug-drug interactions.
- To determine whether accumulation of renally-excreted antiretroviral drugs (e.g. tenofovir) increases their potential to cause renal injury in older HIV-positive people.

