8.2 Methods and planned analysis for pharmacokinetic analyses

Plasma drug concentrations from the older HIV-positive cohort will be compared with suggested minimally effective concentrations of each drug and to data from a large sample of historical HIV-positive controls obtained from a large therapeutic drug monitoring database held by the University of Liverpool. As plasma drug concentrations have a skewed distribution, non-parametric methods (e.g. Mann-Whitney tests) will be used. Proportional hazards regression will be used to investigate the impact of drug concentrations on time to virological failure (defined as two consecutive viral loads >50 copies/ml whilst remaining on treatment) after controlling for other confounders and adherence. All co-medications and drug doses, regardless of the prescriber, will be documented and the potential for drug-drug interactions investigated. Drug interactions will be defined as clinically significant (severe – drugs should not be co administered / potential interaction where dose adjustment may be necessary) or minor, and associations determined with any side effects reported.

Sample size

Based on current treatment guidelines, we anticipate that around 90% of older HIV-positive participants (n=810) will be receiving cART, with 60% of these patients (n=486) receiving tenofovir. These sample sizes are in excess of those generally used for other published studies of antiretroviral pharmacokinetics, providing further scope for multivariable analyses

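### The only between-group contrast of drug concentrations named in section 8.2 is with historical controls of unstated age, which does not fit the older-versus-younger objective in section 4.3

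*Combined protocol and SAP*

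**What the plan says.** Aim 2 in section 4.0 begins "To evaluate associations between antiretroviral drug concentrations and age". Section 4.3 turns it into an objective: to describe concentrations "at baseline in the older HIV-positive cohort, and to compare these to those seen in younger HIV-positive patients".

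Section 8.2 is the methods section for these analyses. It sets the older cohort's concentrations against two references. One is the minimally effective concentration of each drug, a fixed threshold. The other is external: the cohort is compared "to data from a large sample of historical HIV-positive controls obtained from a large therapeutic drug monitoring database held by the University of Liverpool". Mann-Whitney or similar tests are proposed because concentrations are skewed. Control for confounders is stated only for the model of time to virological failure. The sample-size paragraph counts older participants only (810 on cART, 486 of them on tenofovir). The younger cohort is not mentioned.

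Three general statements bear on the point. Section 8.2 closes by saying that its numbers leave room for multivariable work. Section 8.3 plans baseline analyses of concentrations in relation to patient characteristics. Section 6.2 times the samples so that sparse data can be modelled.

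**The concern.** The objective asks whether concentrations differ between older and younger people with HIV. The named contrast answers a different question: whether the older cohort differs from people in a drug-monitoring database. Section 8.2 does not say that these people are younger, how they came to be sampled, or how long after a dose. An unadjusted rank test cannot separate age from any of these. If the controls include people aged 50 or over, a true age difference would also be diluted.

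The protocol itself gives reasons to care. Section 3.2 reports that "Plasma concentrations of some HIV protease inhibitors are higher in those aged >40 years", so the age mix of a control group matters. Section 3.3 criticises other studies as "hampered by the lack of appropriately selected and matched control groups, which limits the conclusions that can be reached". At stake is whether aim 2 gets an interpretable answer. The planned analyses of virological failure and drug interactions are not affected.

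**Working it through.** **1. Objective against method.**

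| Element | Objective (4.3) | Named contrast (8.2) |
|---|---|---|
| Index group | Older HIV-positive cohort, baseline | Older HIV-positive cohort |
| Comparator | Younger HIV-positive patients | Historical HIV-positive controls, age not given |
| Time after dose | – | Not given for controls |
| Adjustment | – | None stated for concentrations |

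The fixed thresholds are not a comparison group, so the historical contrast is the only between-group one.

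**2. Is a better comparator available?** Section 5.2 lists plasma for pharmacokinetics at Visit 1 without restricting it to the older cohort. Section 6.2 aims for at least 5 hours after the dose and records dose time, sample time and food. Section 4.2.1 has younger patients "sampled from these lists at a rate determined by the demographic profile of the older patients at the clinic".

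**3. The plan's own figures.** 90% of 1000 is 900, not 810. The figure 810 equals 0.90 × 900, which suggests a 10% loss (0.90 × 1000 = 900) that section 8.2 does not state. Section 8.1 shows the same pattern: 540 / 0.40 = 1350 = 0.90 × 1500. The loss is therefore an inference. The next step reproduces: 0.60 × 810 = 486 on tenofovir.

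**4. Feasibility for tenofovir (illustration).** Assumptions: the same 10% loss in the younger cohort; 74% of it on cART, which Table 1 gives for clinic patients aged 16–49 in 2008/09; 60% of these on tenofovir, as for the older cohort; two-sided 5%; unadjusted t-test on log concentration.

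- Younger on tenofovir: 500 × 0.90 × 0.74 × 0.60 = 199.8, about 200.
- Standard error in SD units: √(1/486 + 1/200) = 0.0840.
- Power for 0.25 SD: Φ(0.25/0.0840 − 1.96) = Φ(1.02), about 84%.
- Detectable at 80% power: (1.96 + 0.842) × 0.0840 = 0.235 SD (0.236 by the t distribution).

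Variations:

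- No loss: 1000 × 0.90 × 0.60 = 540 against 500 × 0.74 × 0.60 = 222. Power is 88%.
- 60% of the younger cohort on cART: 450 × 0.60 × 0.60 = 162. Standard error √(1/486 + 1/162) = 0.0907; power Φ(0.80), about 79%.
- Mann-Whitney (efficiency 3/π) with 486 against 200: 83%.

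**5. Less-used drugs.** If 30%, 20% or 10% of those on cART take a drug (assumed shares), the groups are about 243 v 100, 162 v 67 and 81 v 33. The differences detectable at 80% power are 0.33, 0.41 and 0.58 SD.

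**6. Age mix of the younger cohort.** Section 4.1 requires at least 150 participants in each of the bands 20–29, 30–39 and 40–49. The 40–49 band therefore holds between 150 and 500 − 150 − 150 = 200 people, or 30% to 40% of the cohort.

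**The case against.** The strongest reply is that the analysis is under-described rather than absent. Section 4.3 speaks of younger patients here, while other objectives speak of cohorts, so the authors may have meant the Liverpool database to supply them. The general wording in sections 8.2 and 8.3 also leaves room for a baseline multivariable analysis in which age is an obvious factor.

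Much of this stands. A reader might infer that the plan rules out an age analysis or that the objective cannot be met; the documents support neither. But section 8.2 does not say that the controls are younger, so the database reading does not show that the objective is met. The general wording names neither age, nor the younger cohort, nor a method.

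A second reply is that the study's own under-50 against 50-plus contrast is also imperfect. This stands too. If levels of some drugs rise from 40, the 30% to 40% of the younger cohort aged 40–49 would dilute it. That favours continuous age over a two-group split; it does not favour the database.

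A third is that the plan is openly descriptive and broad. That is fair, but section 8.2 does choose a comparator and a test, and the comparator is not shown to fit the objective.

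**Conclusion.** The point holds in this form: the one between-group contrast that section 8.2 names for concentrations does not fit the objective, and followed as written it cannot separate age from sample source or sampling time. It should be fixed, because a concrete and better comparator is already in the study. The conclusion rests on the text and needs none of the power figures.

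Those figures show only feasibility: 79% to 88% power for 0.25 SD with tenofovir, depending on the assumed loss and share on cART. The loss, the 74% on cART and the younger cohort's tenofovir share are assumptions, and an adjusted model would not have exactly this power. A reader might want a figure for the bias or dilution against the database. The documents say nothing about its age mix or sampling, so none can be given.

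**What to change.** In section 8.2, name the study's own younger HIV-positive cohort as the main comparator, drug by drug at baseline. Prefer age as a continuous variable across both HIV-positive cohorts. Use regression on log concentration, or the sparse-data model foreseen in section 6.2. Adjust for time since dose, food and the demographic sampling factors (sex, ethnicity, sexual orientation, clinic).

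Report results with and without adjustment for dose and regimen. Section 3.2 suggests that dose needs may differ with age, so dose may lie on the path from age to concentration, and the dose-adjusted result should not be called the total age comparison. A further model with weight, renal function and co-medication is optional. It would address mechanism, since section 3.2 says "Altered body composition and impaired renal function contribute to altered pharmacokinetics and pharmacodynamics in older patients" and that "older HIV-positive people may be treated with several therapeutic agents that may interact with antiretroviral drugs".

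Keep the database as a secondary descriptive comparison and report its age range, selection and sampling times. Give the expected younger numbers for each drug.

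The cost is wording and some modelling. Samples, dose and sampling times, food, weight, co-medication and routine renal tests are already recorded. The main downside is a smaller comparator, especially for less-used drugs. For the optional model, section 5.2 allows renal tests to be up to a year old.

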8.3 Analysis plan

Cross-sectional analyses of clinical manifestations and therapeutic drug concentrations, and their association with patient factors, will be undertaken at the start of the project once baseline visits are complete; analyses of associations with outcomes will be performed in the following years.

8.4 Study management groups

Study Steering Committee (SSC)

The SSC will include all co-applicants, as well as a patient representative and the study co-ordinator. The SSC will meet twice-yearly. The SSC will have responsibility for the overall progress of the study, and providing scientific oversight.

Study Management Team (SMT)

A SMT will be set up to facilitate the efficient coordination of the programme of work. This group will include members of the SSC as well as the study coordinator, the study research nurses, and a community representative. The roles of this group will be to: develop the full study protocol; coordinate ethics approval of the study; develop information sheets for potential participants; over-see the development of all data collection tools; work with local consultants to generate lists of eligible HIV-positive subjects at each clinic; develop strategies and materials

for the recruitment of HIV-negative subjects; monitor patient recruitment and identify potential problems with this at an early stage of the study; and monitor participant retention in the project and develop strategies for maximizing this.

The SMT will meet monthly, either face-to-face or by teleconference.

8.5 Dissemination of study findings

Study results will be published in peer-reviewed journals from 2013 and will be presented at national and international meetings. Members of the team contribute to the development of management guidelines for those with HIV through BHIVA, the Infectious Diseases Society of Ireland (IDSI) and the European AIDS Clinical Society (EACS). Through these groups, we will ensure that all relevant stakeholders receive information on study outcomes. Full anonymity of subject's details will be maintained throughout and no individual patient data will be presented.

Through the involvement in the study of [name], information will be actively disseminated to the HIV patient community; we anticipate that this will involve a combination of workshops/presentations at UK-CAB meetings, the development of posters and short reports of study findings written specifically for the HIV community and to be displayed in hospital waiting areas, and the development of web-based reports accessible through the i-Base website. Subjects wanting to see the results of the study will also be able to request a copy of any study publications from the investigators once they have been published.

A full publication policy, including timelines for receipt of feedback and guidelines for authorship, will be established by the SSC at the start of the study.

8.6 Data sharing policy

We will be proactive in ensuring that this valuable resource is used to its full potential. The SSC will welcome proposals for collaborations from other academic groups as well as the study funders. Those potentially interested should submit a proposal to the SSC containing information about the project, analysis plan and data requirements. Proposals will then be discussed by the SSC and will be approved if it is felt to be scientifically valid with appropriate methodology.

8.7 Role of funders

Funders will also receive an annual report that will include key findings from the study over the past year. The funders will not have any input in the decision to publish findings from the study nor in the content or wording of any submitted manuscripts.

Funders will be allowed to submit scientific research proposals utilising the study data and/or stored samples (potentially requiring further funding) through the channel described above (section 8.6).

APPENDIX 1 TO PROTOCOL

Study questionnaires

The Lawton Instrumental Activities of Daily Living Scale

Ability to Use Telephone

1. Operates telephone on own initiative; looks up and dials numbers.....	1
2. Dials a few well-known numbers.....	1
3. Answers telephone, but does not dial.....	1
4. Does not use telephone at all.....	0

Shopping

1. Takes care of all shopping needs independently	1
2. Shops independently for small purchases.....	0
3. Needs to be accompanied on any shopping trip	0
4. Completely unable to shop.....	0

Food Preparation

1. Plans, prepares, and serves adequate meals independently.....	1
2. Prepares adequate meals if supplied with ingredients.....	0
3. Heats and serves prepared meals or prepares meals but does not maintain adequate diet.....	0
4. Needs to have meals prepared and served.....	0

Housekeeping

1. Maintains house alone with occasion assistance (heavy work).....	1
2. Performs light daily tasks such as dishwashing, bed making.....	1
3. Performs light daily tasks, but cannot maintain acceptable level of cleanliness	1
4. Needs help with all home maintenance tasks.....	1
5. Does not participate in any housekeeping tasks.....	0

Laundry

1. Does personal laundry completely	1
2. Launders small items, rinses socks, stockings, etc.....	1
3. All laundry must be done by others	0

Mode of Transportation

1. Travels independently on public transportation or drives own car.....	1
2. Arranges own travel via taxi, but does not otherwise use public transportation	1
3. Travels on public transportation when assisted or accompanied by another	1
4. Travel limited to taxi or automobile with assistance of another.....	0
5. Does not travel at all.....	0

Responsibility for Own Medications

1. Is responsible for taking medication in correct dosages at correct time	1
2. Takes responsibility if medication is prepared in advance in separate dosages.....	0
3. Is not capable of dispensing own medication	0

Ability to Handle Finances

1. Manages financial matters independently (budgets, writes checks, pays rent and bills, goes to bank); collects and keeps track of income.....	1
2. Manages day-to-day purchases, but needs help with banking, major purchases, etc	1
3. Incapable of handling money	0

Scoring: For each category, circle the item description that most closely resembles the client's highest functional level (either 0 or 1).

ADHERENCE QUESTIONNAIRE

ADHERENCE ASSESSMENT

'We would like to know how much of your HIV medication you have taken recently. We understand that many people on HIV medication find it very difficult to take it regularly and often miss doses so we won't be surprised if you have missed lots of doses as well. We need to know how many doses you have missed.'

This questionnaire is completely confidential. Under no circumstance will your answers be shown to your doctor or anyone else involved with your care.'

QA How many doses of HIV medication did you miss yesterday?

- 0
- 1
- 2

- 3
- Don't know

QB How many doses of HIV medication did you miss the day before yesterday?

- 0
- 1
- 2

- 3
- Don't know

QC How many doses of HIV medication did you miss the day before that? (3 days ago)

- 0
- 1
- 2

- 3
- Don't know

QD How many doses of HIV medication have you missed in the last 2 weeks?

- 0
- 1
- 2
- 3-5
- 6-10

- 11-20
- 20-40
- More than 40
- All of them
- Don't know

QE Put a cross on the line below at the point showing your best guess about how much HIV medication you have taken in the last month. We would be surprised if this was 100% for most people.

e.g. 0% means you have taken no HIV medication

50% means you have taken half your HIV medication

100% means you have taken every single dose of your HIV medication

QF When was the last time you missed a dose of HIV medication ?

- Today
- Yesterday
- Earlier this week
- Last week

- Less than a month ago
- More than a month ago
- Never
- Don't know

STUDY NUMBER:
PATIENT INITIALS:
DATE:
VISIT:

Questionnaire

Thank you for taking the time to fill in this questionnaire.

If you would like help with filling in the questionnaire, one of the study team will be happy to help you.

All information that you give will be treated as strictly confidential.

The nursing team will not assess your answers, they will be entered anonymously at Imperial College.

Take your time – it is not a competition.

Your answers are very important to the POPPY study.

They will give us a good idea how we may treat people as they get older.

The questions will take about 30 minutes to answer.

INSTRUCTIONS

Fill out your answers with a black pen provided – put a cross in the box which most fits your response. The boxes vary in size.

COGNITIVE COMPLAINTS		Never	Hardly ever	Yes, definitely
Q1	Do you experience frequent memory loss (for example, do you forget the occurrence of special events even the more recent ones, appointments etc.)?			

Q2	Do you feel that you are slower when reasoning, planning activities, or solving problems?			
Q3	Do you have difficulties paying attention (for example to a conversation, a book, or a movie)?			

IN GENERAL:

Q4	In general, would you say your health is:	Excellent	Very good	Good	Fair	Poor

Q5	Compared to one year ago, how would you rate your health in general now?	Much better now than one year ago	Somewhat better now than one year ago	About the same as one year ago	Somewhat worse now than one year ago	Much worse now than one year ago

SPECIFICALLY:

The following items are about activities you might do during a typical day. Does your health now limit you in these activities? If so, how much?

		Yes, limited a lot	Yes, limited a little	No, limited not at all
Q6	Vigorous activities, such as running, lifting heavy objects, participating in strenuous sports			
Q7	Moderate activities, such as moving a table, pushing a vacuum cleaner, bowling, or playing golf			
Q8	Lifting or carrying groceries			
Q9	Climbing several flights of stairs			
Q10	Climbing one flight of stairs			
Q11	Bending, kneeling or stooping			
Q12	Walking more than a mile			
Q13	Walking several blocks (say 150 yards)			

Q14	Walking one block (say 50 yards)			
Q15	Bathing or dressing yourself			

IN THE PAST 4 WEEKS:

During the past 4 weeks, have you had any of the following problems with your work or regular daily activities as a result of your physical health?		Yes	No
Q16	Cut down the amount of time you spent on work or other activities		
Q17	Accomplished less than you would like		
Q18	Were limited in the kind of work or other activities		
Q19	Had difficulty performing the work or other activities (for example, it took extra effort)		

FEELINGS OF ANXIETY OR DEPRESSION:

During the past 4 weeks, have you had any of the following problems with your work or other regular daily activities as a result of any emotional problems (such as feeling depressed or anxious)?		Yes	No			
Q20	Cut down the amount of time you spent on work or other activities					
Q21	Accomplished less than you would like					
Q22	Didn't do work or other activities as carefully as usual					
Q23	During the past 4 weeks, to what extent have your physical health or emotional problems interfered with your normal social activities with family, friends, neighbours, or groups?	Not at all	Slightly	Moderately	Quite a bit	Extremely

PAINS:

Q24	How much bodily pain have you had during the past 4 weeks?	None	Very Mild	Mild	Moderate	Severe	Very severe
Q25	During the past 4 weeks, how much did pain interfere with your normal work (including both work outside the home and housework)?	Not at all	slightly	moderate	Quite a bit	Extremely	

You have completed a third of the questions.
Well done!

HOW ARE YOU FEELING?

These questions are about how you feel and how things have been with you during the past 4 weeks. For each question please give the one answer that comes closest to the way you have been feeling:

		All of the time	Most of the time	A good bit of the time	Some of the time	A little of the time	None of the time
Q26	Did you feel full of pep (energy)?						
Q27	Have you been a very nervous person?						
Q28	Have you felt down in the dumps that nothing could cheer you up?						
Q29	Have you felt calm and peaceful?						
Q30	Did you have a lot of energy?						
Q31	Have you felt downhearted and blue?						
Q32	Did you feel worn out?						
Q33	Have you been a happy person?						
Q34	Did you feel tired?						

Q35. During the past 4 weeks, how much of the time have your health or emotional problems interfered with your social activities (like visiting with friends, relatives etc)?

		All of the time	Most of the time	Some of the time	A little of the time	None of the time

GENERAL HEALTH:

How TRUE or FALSE is each of the following statements to you?					
	Definitely true	Mostly true	Don't know	Mostly false	Definitely false
Q36 I seem to get sick a little easier than other people?					
Q37 I am as healthy as anybody I know					
Q38 I expect my health to get worse					
Q39 My health is excellent					

DEPRESSION:

During the past week

	Rarely or none of the time (less than 1 day)	Some or a little of the time (1-2 days)	Occasionally or a moderate amount of time (3-4 days)	Most or all of the time (5-7 days)
Q40 I was bothered by things that usually don't bother me				
Q41 I did not feel like eating: my appetite was poor				
Q42 I felt that I could not shake off the blues even with help from my family or friends				
Q43 I felt I was just as good as other people				
Q44 I had trouble keeping my mind on what I was doing				
Q45 I felt depressed				
Q46 I felt that everything I did was an effort				
Q47 I felt hopeful about the future				
Q48 I thought my life had been a failure				
Q49 I felt fearful				
Q50 My sleep was restless				
Q51 I was happy				

Q52	I talked less than usual				
Q53	I felt lonely				
Q54	People were unfriendly				
Q55	I enjoyed life				
Q56	I had crying spells				
Q56a	I felt sad				
Q57	I felt that people dislike me				
Q58	I could not get "going"				

Over the last 2 weeks, how often have you been bothered by

		Not at all	Several days	More than half the days	Nearly every day
Q59	Little interest or pleasure in doing things				
Q60	Feeling down, depressed or hopeless				
Q61	Trouble falling asleep, staying asleep, or sleeping too much				
Q62	Feeling tired or having little energy				
Q63	Poor appetite or overeating				
Q64	Feeling bad about yourself – or that you're a failure or have let yourself or your family down				
Q65	Trouble concentrating on things, such as reading the newspaper or watching television				
Q66	Moving or speaking so slowly that other people could have noticed. Or the opposite – being so fidgety or restless that you have been moving around a lot more than usual				
Q67	Thoughts that you would be better off dead, or of hurting yourself.				

RISK OF FALLING:

Q68	Over the past 28 days have you had any falls?	I have not fallen	Once	Twice	Three or more times

If you have had no falls please do not answer the next few questions and proceed to question 73, otherwise please answer the next question.

Where have you fallen?

Q69	Inside You may tick more than one	On the one level	
		Getting out of bed	
		Getting out of a chair	
		Using the shower/bath	
		Using the toilet	
		Walking up or down stairs	
		Other	
	Home entrance or in the garden You may tick more than one	Walking up or down a step	
		On the one level (e.g path)	
		In the garden	
		Other	
	Away from home: You may tick more than one	On the footpath	
		On a kerb/gutter	
		In a public building	
		Getting out of a vehicle	
		In another person's home	
		Other	

Q70	How did you fall? Tick more than one if necessary							
	I tripped	I slipped	I lost my balance	My legs gave way	I felt faint	I felt giddy/dizzy	I am not sure	Other
Q71	As a result of this fall or falls did you suffer any injuries?				Yes	No		

Q72 If yes, what type of injuries did you suffer?						
Bruises	Cuts/grazes	Broken wrist	Broken hip	Broken ribs	Back pain	Other

--	--	--	--	--	--	--

[figure not shown]
[figure not shown]
[figure not shown]
ACHES AND PAINS

Q73	During the past month have you had any aches or pains which have lasted for one day or longer?	Yes	No

if YES, please continue with question 74, otherwise go to question 78

		Yes	No
Q74	Do you have any such aches or pains today?		
Q75	If you work - did you miss any days in the past month from work because of aches or pains? LEAVE BLANK IF YOU DO NOT WORK		
Q 76	Have you previously consulted your family doctor because of these aches or pains?		

Q77 Please shade any area on the diagrams below where you feel, or have felt, aches and pains during the past month:

EMPLOYMENT, EDUCATION AND HOUSING

Q78	What is your current work situation?	cross one square only
	Employed or self-employed FULL-TIME (at least 30 hours per week)	

Employed or self-employed PART-TIME (less than 30 hours per week)	
Full time student / education / training	
Unemployed and registered for benefits	
Unemployed, NOT registered for benefits	
Permanently sick / disabled (for 3 months or more)	
Temporarily sick / disabled (for less than 3 months)	
Looking after home / family / dependants full-time	
Retired	
Other (please specify)	
If you work, or are a full time student, or you have been temporarily sick or disabled (for less than 3 months), how many days have you been off sick in the last year?	Enter number below

Q79	What is your current housing situation?	cross one square only
	Own my own home (including with mortgage / loan / shared ownership)	
	Renting from the council or housing association	
	Renting from private landlord	
	Temporary accommodation (hostel, shelter, bed & breakfast, squat)	
	Staying with partner / friend(s) / family	
	Homeless	
	Other (please specify)	

Q80	Do you have enough money to cover your basic needs? (e.g. food, heating)	cross one square only
	Yes, all of the time	
	Yes, most of the time	
	Yes, some of the time	

No	
----	--

Q81	At what level did you COMPLETE your education? (Please tick ONE ONLY)	cross one square only
	Finished education with no qualifications	
	O levels / GCSEs (or equivalent qualifications at age 16)	
	A levels (or equivalent qualifications at age 18)	
	University degree or above	
	Other qualifications (please specify)	

SEXUAL FUNCTION

Q82	Regarding your sexuality: which of the following options best describes how you think of yourself?	cross one square only
	Gay or homosexual	
	Bisexual	
	Straight or heterosexual	
	Any other term (please state)	
	I don't usually use a term	

Q83	How often have you felt unsatisfied with your own sex life during the last 4 weeks?	cross one square only
	Never	
	Rarely	
	Now and then	
	Often	
	Always	

Q84	How often have you worried about minimal sexual desire during the last 4 weeks?	cross one square only
	Never	

Rarely	
Now and then	
Often	
Always	

IF YOU ARE MALE PLEASE ANSWER THE FOLLOWING QUESTION. MALES ONLY PLEASE.

Q85	How often could you develop an erection while being sexually active during the last 4 weeks?	cross one square only
	I haven't been sexually active / not applicable	
	Nearly always or always	
	Most of the times (much more than half of the times)	
	Sometimes (approximately half of the times)	
	A few times (much less than half of the times)	
	Almost never or never	

IF YOU ARE FEMALE PLEASE ANSWER THE FOLLOWING QUESTIONS. FEMALES ONLY PLEASE.

Q86	How often have you been satisfied about your sexual arousal during sexual activities or sexual intercourse during the last 4 weeks?	cross one square only
	I haven't been sexually active / not applicable	
	Nearly always or always	
	Most of the times (much more than half of the times)	
	Sometimes (approximately half of the times)	
	A few times (much less than half of the times)	
	Almost never or never	

Q87. Relating to women's periods.

Usually women's periods stop in their 40s or 50s. This is known as the **menopause** or '**the change**'. Some women experience physical and emotional symptoms as their periods begin to stop and for some time after. We want to ask a few questions to find out how this may affect you.

Section A:

Factors affecting cycle.

(please tick the appropriate box)

1. In the past 6 months have you used	Yes	No	Don't Know
The contraceptive implant (Nexplanon).			
The contraceptive injection (Depo or Depo-provera),			
The hormone coil (Mirena),			

The contraceptive pill?			
2. In the past 12 months have you been pregnant or breastfed?			
3. Are you currently having treatment for any type of cancer?			

If yes please give details of the cancer and any treatment.

4. Have you had your ovaries and/or uterus (womb) removed?			
--	--	--	--

Section B:
Menstrual pattern.

1. When was your last period?	Month (if known)...../Year.....
2. Thinking about your periods, which of the following best applies to you (tick one):	
a. I have had regular periods in the past 3 months.	a
b. I have had periods in the past 3 months but they are irregular.	b
c. My last period was more than 3 months ago but less than 12 months ago.	c
d. I have not had a period for between one to two years.	d
e. I have not had a period for over two years.	e
